BP	blood pressure
BPM	blood pressure monitoring
BUN	blood urea nitrogen
C _{max}	maximum concentration
CKD	chronic kidney disease
CMV	cytomegalovirus
CRF	case report form
CRP	C-reactive protein
CT	computed tomography
CTCAE	Common Terminology Criteria for Adverse Events
DBP	diastolic blood pressure
ECG	electrocardiogram
eCRF	electronic Case Report Form

ED ₅₀	50% effective dose
eGFR	estimated glomerular filtration rate
FSH	follicle stimulating hormone
GalNAc	N -acetyl galactosamine
GCP	Good Clinical Practice
HAV	hepatitis A virus
HBsAg	hepatitis B surface antigen
HBV	hepatitis B virus
HCV	hepatitis C virus
HepB	hepatitis B
HIV	human immunodeficiency virus
HR	heart rate
hr, hrs	hour(s)
hsCRP	CRP measured by high sensitivity assay
HTN	hypertension
ICH	International Conference on Harmonization
IgM	immunoglobulin M
INR	international normalized ratio
IRB	Institutional Review Board
IRT	Interactive Response Technology
IV	intravenous(ly)
KIM-1	kidney injury molecule 1
LLN	lower limit of normal
m ²	square meter
MCH	mean corpuscular hemoglobin
MCHC	mean corpuscular hemoglobin concentration
MCV	mean corpuscular volume
MedDRA™	Medical Dictionary for Regulatory Activities
min	minute
mm	millimeter
mmHg	millimeter mercury
MRI	magnetic resonance imaging

ISIS 757456-CS2
Protocol

CONFIDENTIAL

Amendment 1
29 March 2019

mRNA	messenger ribonucleic acid
NAG	N -acetyl- β D-glucosaminidase
NCS	not clinically-significant
NGAL	neutrophil gelatinase-associated lipocalin
NOAEL	No Adverse Effect Level
NYHA	New York Heart Association
on study	The subject is 'on study' from signing of the informed consent until their last study visit
P/C	protein/creatinine
PD	pharmacodynamic(s)
PH	measure of the acidity or basicity of a solution
PK	pharmacokinetic(s)
PPS	per protocol population
pRBC	packed red blood cells
PT	prothrombin time
RAAS	renin-angiotensin-aldosterone system
RHTN	resistant hypertension
RNase H1	an ubiquitous endonuclease that specifically hydrolyzes the RNA strand in RNA/DNA hybrids
q.d.	daily
RR	respiration rate
SAE	serious adverse event
SAP	statistical analysis plan
SBP	systolic blood pressure
siRNA	small interfering ribonucleic acid
SC	subcutaneous(ly)
Study Day 1	defined as the first day Study Drug product is administered to the patient
Study Drug	ISIS 757456 or placebo
SUSAR	suspected unexpected serious adverse reaction
TEAE	treatment-emergent adverse event
T _{max}	time to maximal concentration
UACR	urine albumin-creatinine ratio
ULN	upper limit of normal

UPCR	urine protein-creatinine ratio
WBC	white blood cell
WO	washout
WOCBP	woman of child-bearing potential

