Study Visit Schedule and Procedures Continued	
Treatment: Week 1 to Week 6
 
After the WO Period, eligible subjects will be stratified based on screening plasma angiotensinogen (AGT) concentration ($\leq 30 \mu\text{g/mL}$ vs $> 30 \mu\text{g/mL}$) and randomized 2:1 to 80 mg ISIS 757456 or placebo. Subjects will receive SC doses of Study Drug on Study Days 1, 3, 8, 15, 22, 29, and 36. Subjects will remain off antihypertensive medications for approximately 3 months throughout the study.
 
Subjects that discontinue treatment may remain in the study and will attend the Study Day 43 visit.
 
Post-Treatment: Week 7 to Week 19
 
Subjects are to return to the Study Center for follow-up visits on Study Days 43, 50, 64, 78, 106 and 127. The final study visit will be Study Day 127 (Week 19).

Primary Endpoint	Percent change in plasma angiotensinogen from Baseline to Study Day 43 (Week 7) compared to placebo
Secondary Endpoints	Change on in-clinic SBP from Baseline to each scheduled, post-Baseline visit Change and percent change in plasma angiotensinogen from Baseline to each scheduled, post-baseline visit
Safety Endpoints	Incidence and severity of treatment-emergent adverse events (TEAE) (including hypotension and orthostatic hypotension), use of concomitant medications, laboratory assessments, ECG, and vital signs

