3. EXPERIMENTAL PLAN

3.1. Study Design

This will be a Phase 2, double-blind, randomized, placebo-controlled study of ISIS 757456 conducted in mild hypertensive subjects on an ACEi/ARB and an additional hypertensive medication (see Section 5.1 Inclusion Criteria). Subjects will be stratified based on a screening plasma AGT concentration ($\leq 30 \mu\text{g/mL}$ vs. $> 30 \mu\text{g/mL}$) and randomized in a 2:1 ratio to receive a once-weekly SC treatment and an additional loading dose on Study Day 3 with either ISIS 757456 80 mg or placebo for 6 weeks (See [Study Design and Treatment Schema](#)).

All subjects will complete a 13-week Post-Treatment Period. In the Post-Treatment Period, should a subject's sitting BP on home monitoring exceed 140 mmHg systolic or 100 mmHg diastolic on 2 consecutive days (confirmed by triplicate measurement at the Study Center), the subject's initial HTN medication(s) may be added back per Investigator and Sponsor Medical Monitor judgment and the subject will continue to be followed per protocol in the study.

Refer to Section 8.1 for additional details.

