6.1.4. Treatment Period

Eligible subjects will be administered Study Drug (ISIS 757456 or placebo) on a weekly basis (6 weeks) as well as an additional dose on Study Day 3 for a total of 7 doses. Review of the at-home blood pressures and the in-clinic BP should be performed prior to administering the Study Drug.

Safety and clinical laboratory evaluations as well as blood sampling for PK analysis will be performed periodically throughout the Treatment Period ([Appendix A](#), [Appendix B](#), and [Appendix C](#)). Any AEs and concomitant medications will be recorded. If antihypertensive medications are re-instated this will be captured in the concomitant medications eCRF. All safety data including AEs, at home and in-clinic BP, and concomitant medications will be reviewed by the Sponsor's Medical Monitor or designee on an ongoing basis throughout the trial.

Subjects will continue at home BP and HR monitoring during the Treatment Period as outlined in Section [6.1.1.3](#) and [Appendix A](#). Subjects who discontinue the Treatment Period early will continue in the study following the post-treatment evaluations (Section [6.1.5](#))

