6.1.5. Post-Treatment Evaluation Period

After the last dose (Study Day 36) or last dose for early termination subjects, subjects will return to the clinic once-weekly for the first 2 weeks (Study Days 43, 50) and then on Study Days 64, 78, 106, and 127 for safety assessments.

Subjects will continue at home BP and HR monitoring during the Post-Treatment Period as outlined in Section [6.1.1.3](#) and [Appendix A](#).

All safety data including AEs, at home and in-clinic BP, and concomitant medications will be reviewed by the Sponsor's Medical Monitor or designee on an ongoing basis throughout the trial.

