8.5. Safety Monitoring Rules

Please refer also to the 'Guidance for Investigator' section of the ISIS 757456 Investigator's Brochure.

In addition to the standard monitoring of clinical safety parameters, the following guidelines are provided for the monitoring of selected parameters chosen based on preclinical and clinical observations.

Confirmation Guidance: At any time during the Study (Treatment or Post-Treatment Periods), the initial clinical laboratory results meeting the safety monitoring criteria presented below must be confirmed by performing measurements (ideally in the same laboratory that performed the initial measurement) on new specimens. All new specimen collections should take place as soon as possible (ideally within 3 days of the initial collection). For stopping rules, if the initial laboratory result is observed during the Treatment Period, the results from the retest must be available prior to administering the next dose of Study Drug (ISIS 757456 or placebo).

Re-dosing Guidance: Subjects with initial laboratory test values that reach a stopping rule must not be re-dosed until the re-test results are available. In general, subjects who do not meet the stopping rules based upon retest may continue dosing. However, the Investigator and the Sponsor Medical Monitor (or appropriately qualified designee) should confer as to whether additional close monitoring of the subject is appropriate. If any of the stopping criteria described below (refer to Section 8.6.1 to Section 8.6.5) are met, the subject will be permanently discontinued from further treatment with Study Drug (ISIS 757456 or placebo), evaluated fully as outlined below and in consultation with the Sponsor Medical Monitor or appropriately qualified designee, and will be followed-up in accordance with Section 8.8.

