8.6.5. Stopping Rule for Blood Pressure

1. In the event of a SBP ≤ 90 mmHg with symptoms of hypotension (i.e., dizziness, light-headedness, clammy skin, fatigue, blurry vision), as measured by home BPM, at any point in the study, the patient should contact the Study Center immediately and have the SBP confirmed by the Study Center. If confirmed and the patient remains symptomatic, dosing of a subject with Study Drug will be interrupted. If patient is still symptomatic after instituting IV hydration (see Section 8.5.3 Safety Monitoring Rules for Blood Pressure), the patient should be admitted to the hospital. Timing for re-institution should be assessed depending on the reversibility of initiating factors (decreased oral intake, cold/flu, other illness). If the subject remains symptomatic Study Drug should be stopped permanently. If this occurs in the follow-up period, any other antihypertensives or other medications that could affect BP should be stopped, if feasible. The use of IV angiotensin II or vasopressors should be considered in subjects that remain symptomatic and are hemodynamically unstable. The subject will continue to be followed per protocol

in the study. Follow-up for subjects that screen fail due to blood pressure inclusion criteria (see Section 5.1) will not be necessary.

2. During the Treatment Period, should a subject experience a BP measurement > 170 mmHg (systolic) or > 110 mmHg (diastolic) a second measurement must be done within a 30-minute period. If the subject's BP is >170 mmHg (systolic) or > 110 mmHg (diastolic) within the 30-minute period, an additional BP measurement should be taken within 48 hours at the Study Center, regardless of whether the initial BP measurements were taken in clinic or at home. If the subject then experiences a BP measurement > 170 mmHg (systolic) or > 110 mmHg (diastolic) (confirmed by triplicate measurement at the Study Center), they will then be withdrawn from further blinded, randomized treatment. The subject's pre-study antihypertensive medication(s) may be added back per Investigator and Sponsor Medical Monitor judgement. The subject will continue to be followed per protocol in the study.

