8.8. Discontinuation of Study Drug

A subject must permanently discontinue study treatment for any of the following:

- The subject withdraws consent
- The subject experiences an AE that necessitates permanent discontinuation of Study Drug
- The subject develops laboratory test abnormalities that meet any of the stopping rules listed in Section 8.6.1 to Section 8.6.3
- The subject experiences an AE that necessitates unblinding of the Investigator to the subject's treatment assignment

The reason for discontinuation of Study Drug treatment must be recorded in the electronic Case Report Form (eCRF) and source documentation.

For subjects withdrawn for reasons other than withdrawal of consent every effort should be made to complete the early termination study procedures and observations at the time of withdrawal (see [Appendix A](#)) and ideally within 2 weeks from the last dose of Study Drug.

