Appendix A Schedule of Procedures *Continued*

Legend Continued

- 6 Stored at -80 °C for follow-up exploration of laboratory findings and/or AEs (e.g., measurement of cytokine and/or chemokine levels, measurement of additional markers of kidney function, measurement of antibodies, etc.) in this or subsequent clinical studies of ISIS 757456
- 7 If the platelet value, serum creatinine or liver enzyme tests are uninterpretable (e.g., due to clumping, hemolysis or quantity not sufficient) a repeat blood specimen should be re-drawn as soon as possible (ideally within 7 days) prior to next dose. Due to time constraints, a local lab draw is recommended if a repeat blood specimen is necessary to continue dosing at any time after Study Day 1 to Study Day 8.
- 8 Height at Screening only
- 9 Subjects who terminate treatment or post-treatment early from the study should be encouraged to participate in an early termination visit, at which time the Study D43 or Study D127 assessments should be conducted, respectively
- 10 Archived samples to be collected as well. Samples will be stored at -80 °C for follow-up exploration of laboratory findings and/or AEs in this or subsequent clinical studies of ISIS 757456
- 11 Fasting is not required at Screening visit. Fasted samples should be taken after fasting for at least 8 hours. During this time the patient can drink water and they should ensure that they consume sufficient water in order to not become dehydrated.

Time (time is in reference to Study Drug administration):

- a Pre-dose
- b Pre-dose, 3hr
- c Pre-dose, 2 hr
- d Pre-dose, 1, 2, 4, 6 hrs post-SC injection

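### The protocol does not settle which visits a subject attends after stopping Study Drug, and an early-termination AGT value could be analysed as Day 43

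*Combined protocol and SAP*

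**What the plan says.** The subject in question stops Study Drug but does not withdraw consent. Leaving study procedures altogether has its own section (Protocol 8.9).

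- Synopsis, Study Visit Schedule and Procedures (Treatment): "Subjects that discontinue treatment may remain in the study and will attend the Study Day 43 visit". Staying is optional, and Day 43 is the only visit named for this group.
- Protocol 6.1.4: "Subjects who discontinue the Treatment Period early will continue in the study following the post-treatment evaluations". Staying is the rule. Protocol 3.1 agrees: "All subjects will complete a 13-week Post-Treatment Period".
- Protocol 6.1.5: "After the last dose (Study Day 36) or last dose for early termination subjects, subjects will return to the clinic once-weekly". The visits it lists are Days 43, 50, 64, 78, 106 and 127.
- Protocol 8.5: a subject who meets any stopping rule "will be followed-up in accordance with Section 8.8". Section 8.8 asks for early-termination procedures at the time of withdrawal and "ideally within 2 weeks from the last dose of Study Drug". It names no later visit.
- Protocol 8.6.5, for subjects taken off treatment for blood pressure: "The subject will continue to be followed per protocol in the study".
- Appendix A, footnote 9: "Subjects who terminate treatment or post-treatment early from the study should be encouraged to participate in an early termination visit". For a subject ending treatment early, the Day 43 assessments are done at that visit. In the schedule table, Treatment Early Term and D43 are one column, scheduled visit 12, with a window of ±2 days.

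On the analysis side, SAP 3.1 summarises data by the visit label in the data and averages results that share a label. SAP 3.3.1 admits a subject to the Per Protocol Set (PPS) with five of the seven doses. SAP 3.3.2 imputes nothing.

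**The concern.** Optional and mandatory continuation cannot both govern the same subject. The pointer from 8.5 to 8.8 adds a third instruction, and no passage says whether the early-termination visit comes on top of the Day 43 to Day 127 schedule or takes its place. Two sites could act differently on the same event, each with text to support it.

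Two things are at stake. First, secondary AGT is compared at every scheduled post-baseline visit in the PPS and the Full Analysis Set without imputation (SAP 3.5.2), so a subject released early is missing from each later visit, along with the scheduled laboratory and vital-sign data. Second, the primary endpoint is percent change in AGT at Day 43. If the early-termination sample carries the Day 43 label, a measurement from another time can enter the primary comparison, alone or averaged with a true Day 43 value. The SAP has no rule against this.

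**Working it through.** **1. The plan's own figure.** Last scheduled dose is Day 36 and final visit Day 127: (127 − 36)/7 = 91/7 = 13.0 weeks. This reproduces the 13-week Post-Treatment Period.

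**2. The passages side by side, for a subject who stops drug early.**

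| Place | Staying in the study | Visits named |
|---|---|---|
| Synopsis | optional | Day 43 |
| 3.1 | all subjects | 13 weeks post-treatment |
| 6.1.4 with 6.1.5 | the rule | Days 43, 50, 64, 78, 106, 127 |
| 8.5 pointing to 8.8 | not stated | one early-termination visit |
| 8.6.5 (blood pressure) | followed per protocol | protocol schedule |
| Appendix A, footnote 9 | one visit encouraged | Day 43 assessments done at that visit |

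**3. Spread in scheduled follow-up.** Between the one visit the synopsis names for discontinuers and the last visit under 6.1.4 and 6.1.5: 127 − 43 = 84 days, whatever the last dose. Five visits lie in that gap: Days 50, 64, 78, 106 and 127.

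**4. When the early-termination sample falls.** With last dose on Day L, the outer target in 8.8 is Day L + 14, which precedes Day 43 by 43 − (L + 14) days. The Day 43 window is Days 41 to 45.

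| Last dose (Day L) | Doses received | 8.8 visit by Day | Days before Day 43 | Meets PPS dose rule |
|---|---|---|---|---|
| 1 | 1 | 15 | 28 | no |
| 3 | 2 | 17 | 26 | no |
| 8 | 3 | 22 | 21 | no |
| 15 | 4 | 29 | 14 | no |
| 22 | 5 | 36 | 7 | yes |
| 29 | 6 | 43 | 0 | yes |

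The row that matters for the primary analysis is last dose Day 22. The subject meets the PPS dose rule, and the visit is due by Day 36, which is 41 − 36 = 5 days before the window opens. For last dose Day 29 the target coincides with Day 43, but 8.8 also asks for the procedures at the time of withdrawal, so that sample may be earlier too.

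**5. Weight of one mislabelled value.** About 30 subjects randomised 2:1 gives 30 × 2/3 = 20 active and 30 × 1/3 = 10 placebo. If all enter the PPS, and ignoring the stratum adjustment, one subject carries 1/20 = 5% of the active mean or 1/10 = 10% of the placebo mean. If the early value and a true Day 43 value share the label, each contributes half of that subject's result.

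**6. How many subjects.** The documents give no discontinuation rate. Assuming 10% to 20%, 3 to 6 of 30 subjects would be involved. At up to five visits each, that is at most 15 to 30 of 30 × 5 = 150 subject-visits after Day 43.

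**The case against.** The strongest reply is that the documents lean one way. Directly after the sentence on discontinuers, the synopsis lists the post-treatment visits through Day 127 with no exception. The synopsis also defers detail to Section 6, where 6.1.4 is mandatory. Section 8.8 never says follow-up ends at the early-termination visit, and it speaks of withdrawn subjects, so the visit can be read as an addition. Section 8.5.4 supports that reading: platelets are monitored for four weeks after discontinuation, to Day 22 + 28 = Day 50 in the example above, past the 8.8 visit.

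Much of this stands, and it rules out several stronger readings that a reader might infer:

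- *Follow-up ends two weeks after the last dose under 8.8* (Day 22 for last dose Day 8). That is a target for one visit, not a documented end of follow-up.
- *Section 6.1.5 means 13 weeks from the subject's own last dose* (8 + 91 = Day 99, or 22 + 91 = Day 113). Section 6.1.5 lists fixed Study Days, and the glossary ties Study Day 1 to the first dose.
- *Adverse-event follow-up is cut short.* Sections 9.4.1 and 9.4.2 run recording to Day 127 without exception.
- *Subjects stopped for blood pressure, platelets, potassium or renal findings are the ones lost.* Section 8.6.5 keeps blood-pressure cases in follow-up, and Sections 8.5.4, 8.6.2, 8.6.3 and 8.6.4 have follow-up provisions of their own. Where antihypertensives are restarted, SAP 3.5.2 removes later blood pressure from the comparison whichever visit rule applies.

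What the reply does not remove is the direct clash between optional and mandatory continuation, the unexplained pointer from 8.5 to 8.8, the shared visit column, and the absence of any SAP rule for early-termination samples.

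**Conclusion.** The inconsistency is real and lies in the current text. Scheduled AGT, laboratory and vital-sign follow-up after stopping drug could differ by up to 84 days and five visits between sites. That is an upper limit: it assumes a site releases the subject after Day 43, which the synopsis permits but does not require. Separately, an AGT value from about Day 36 or earlier could be analysed as, or averaged into, Day 43 for a PPS subject. That assumes the early-termination visit is recorded under the shared Day 43 label. The effect on the treatment estimate cannot be computed from the documents, but with about 20 and 10 subjects per arm one case is not negligible. No sample-size or power figure changes. This should be corrected, but it does not undermine the design.

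**What to change.** In the protocol, reconcile the synopsis sentence, 6.1.4, 6.1.5, 8.5, 8.8 and Appendix A footnote 9 to one visit rule that keeps stopping Study Drug distinct from leaving the study. Sections 3.1 and 6.1.4 already state continued follow-up; the sponsor should confirm that this is the intent. State in 6.1.5 that Study Days are counted from Day 1 for all subjects, and say whether the early-termination visit is additional to the later schedule. Section 8.8 should not simply be restricted to subjects leaving the study: 8.5 relies on it for subjects who meet a stopping rule, so the pointer and its target must be revised together.

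In the SAP, give early-termination assessments taken outside Day 43 ± 2 days their own visit label, so that they are listed but neither enter nor are averaged into the Day 43 analysis.

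The cost is wording in six places at the next amendment and one SAP sentence. If continued follow-up is confirmed, the few subjects who stop drug attend a few more visits, all of them already in the schedule.

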1. OBJECTIVES AND ENDPOINTS

1.1. Objectives

1.1.1. Primary Objectives

- To evaluate the effect of ISIS 757456 subcutaneous (SC) injection on plasma angiotensinogen concentration

1.1.2. Secondary Objectives

- To evaluate the effect of ISIS 757456 on in-clinic systolic blood pressure over time in Treatment and Post-Treatment Periods

1.1.3. Safety Objectives

- To evaluate the safety and tolerability of ISIS 757456 vs. placebo

1.1.4. Exploratory Objectives

- To evaluate the effect of ISIS 757456 on at-home blood pressure over time in the Treatment and Post-Treatment Periods
- To evaluate the exploratory effects of ISIS 757456 administered subcutaneously {e.g., angiotensin II, renin [Plasma renin activity (PRA); active renin mass concentration (ARC)], plasma aldosterone}
- To evaluate the pharmacokinetics (PK) of ISIS 757456 (as total Full Length ASO, including fully conjugated, partially conjugated, and unconjugated ISIS 757456) administered subcutaneously in subjects with hypertension
- To evaluate potential PK/PD correlation with relevant biomarkers

1.2. Study Endpoints

1.2.1. Primary Endpoints

- Percent change in plasma angiotensinogen from Baseline to Study Day 43 (Week 7) compared to placebo

1.2.2. Secondary Endpoints

- Change on in-clinic SBP from Baseline to each scheduled, post-Baseline visit
- Change and percent change in plasma angiotensinogen from Baseline to each scheduled, post-baseline visit

